The Violence, Evidence, Guidance, Action (VEGA) Education Resources¹ are a novel education intervention that has the potential to improve the preparation of healthcare and social service providers (HHSPs) to be able to effectively recognize and respond to IPV and related forms of family violence, including child maltreatment (CM), in their clinical encounters. VEGA resources were developed based on systematic reviews and consultation with individuals belonging to 22 national healthcare and social service organizations, including the Royal College of Physicians and Surgeons of Canada (see www.vegaproject.mcmaster.ca). VEGA resources follow a competency-based framework and a participatory, encounter-based curriculum that includes four learning modules: (a) the epidemiology of IPV and CM; (b) strategies for safely recognizing and responding to (i) IPV and (ii) CM; and (c) principles for ensuring safe clinical encounters for IPV and CM discussions. VEGA can be completed as a self-directed learning opportunity or in a workshop that is led by two trained facilitators; both approaches take approximately 3.5 hours to complete. *Importantly, neither of the VEGA educational approaches have been evaluated as an adjunct to standard HSSP education for improving HSSP knowledge and skills related to IPV.*

¹Used with permission from the VEGA Project.

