2.2.1 Eligibility and Screening

Study participants will be recruited from a population of veteran-serving HSSPs working within programs, agencies, and organizations recommended by the Atlas Institute for Veterans and Families, examples include the Veteran Affairs Canada (VAC) Assistance Service, the Veteran Family Program, or the Operational Stress Injury Clinics. These contacts will be within Atlas' and the research team's professional networks. Direct recruitment of providers will also take place via social media accounts of research team members and partnering agencies [see CoE_VEGA_Social Media Drafts_V2_10APR2023]. Veteran-Serving HSSPs are eligible for inclusion if:

- i. They are healthcare or social service professionals.
- ii. They are working with military and/or RCMP veterans or military and/or RCMP veteran's family members in a direct service capacity at least one day per week OR they have at least two years or more of experience working with military and/or RCMP veterans or their family members in a direct service capacity OR they have worked with 15 or more patients that were either military and/or RCMP veterans or their family members in a direct service capacity.
- iii. They are willing and capable of providing informed, written consent and completing all project activities in English.

Exclusion Criteria: HSSPs who have previously registered to access VEGA materials; HSSPs who are currently enrolled in or expected to enroll in any other educational intervention focused on family violence (intimate partner violence, child maltreatment, childhood exposure to IPV) within the study time period.

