2.2.2 Informed Consent

Once a provider has initiated contact with the research team, the research assistant (RA) will, depending on the participant's preference, either arrange a telephone call to discuss the study and ask eligibility and demographic screening questions or send them a link to the screening & demographics questionnaire hosted on REDCap [see “Step 3: Initial Contact from Participant & Arranging Screening and Demographics Questionnaire” in “CoE_VEGA_EmailScripts_V8_12MAY2023”]. During the call, the RA will first give a short description of the training and research components of the study with the opportunity of providers to ask questions. If participants choose to self-complete the questionnaire online, there will also be a short description of the study before participants complete the questionnaire on REDCap. The screening and demographics questionnaire will contain a series of questions to determine the eligibility of providers for the study, defined by the inclusion and exclusion criteria above. It will also ask a series of sociodemographic questions [for eligibility and demographic questions, see “Appendix A: Screening Eligibility and Demographic Questionnaire REDCap Form” in “CoE_VEGA_ScreeningCallScript_V7_03APR2023”]. If completing measures over the phone, the provider's answers will be entered by the RA into REDCap. We will obtain written consent from providers to keep their responses to the screening and demographics questionnaire should they end up being ineligible or do not end up participating in the study. This is for the purpose of comparing those who end up participating to those who do not end up participating to understand

Centre of Excellence VEGA Training and Research Project

if our criteria are potentially excluding a particular group of people or if those who do not end up participating belong to a particular group.

After completing the eligibility and demographic questions, providers will be informed of their eligibility for the study. This communication will occur via phone [see pg. 2-3 of CoE_VEGA_ScreeningCallScript_V7_03APR2023] or email [see pg. 4-5 of CoE_VEGA_EmailScripts_V8_12MAY2023] based on the participant's preference.

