2.2.4 Education Intervention

Self-Directed VEGA – Experimental Arm uses an approach where participants complete the Violence, Evidence, Guidance, Action Project (VEGA) content online as a self-directed educational activity, at their own pace in a series of modules. Individuals will register to access the VEGA Education Resources site at <https://vegaproject.mcmaster.ca/>. Registration will be free. They will be asked to provide their name and email to be sent the online resources. They will also be asked to agree to terms of use to access this site. Participants will be sent an information sheet that outlines the steps to register and access the VEGA materials online [“CoE_VEGA_SelfDirectedRegistration_V6_03MAR2023.”]. Participants have the option of completing the self-directed VEGA arm in either English or French as the VEGA Educational Resources site offers the content in French and English. The consent form will inform participants this is an option for the self-directed VEGA arm only. The information sheet for registering for self-directed VEGA will also show participants how to access the French version of the VEGA online modules [CoE_VEGA_SelfDirectedRegistration_V6_03MAR2023.”].

Participants will be asked to direct all content-related questions to the RC who will forward them to the VEGA team to see if they can be answered. Participants will be provided the contact information for the VEGA IT Team who will address any technology-related questions they may have while completing the self-directed VEGA program [see “RISE with Veteran Service Providers – Training Program Assignment” in CoE_VEGA_EmailScripts_V8_12MAY2023]. If they haven’t completed them already, participants will receive reminders via email every two days from the RC reminding them to complete the self-directed VEGA online modules [see “RISE with Veteran Service Providers – Online Modules Reminder” in CoE_VEGA_EmailScripts_V8_12MAY2023”].

Participants will be asked to complete the self-directed VEGA at their convenience, within one week of when they are informed they have been asked to complete the self-directed VEGA program. It will take approximately 3 hours for participants to complete all modules.

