Facilitator-Led VEGA – Active Control Arm uses a group-based approach where participants complete the Violence, Evidence, Guidance, Action Project (VEGA) content as a virtual or face-to-face workshop (i.e., *facilitator-led VEGA*). In this study, all workshops will be virtual to prevent social gathering during COVID-19. The AC intervention will be facilitated via Zoom technology, by two trained facilitators with between 15 to 20 participants in each workshop (keeping the recommended 10:1 participant-to-facilitator ratio) and will last approximately 3 hours. The workshop approach is delivered by trained facilitators and is standardized via the use of a flexibly structured facilitator's guide.

As of March 2023, no participants will be asked to complete facilitator-led VEGA, as we are removing this arm from the study.

VEGA training takes approximately 3 hours to complete and pedagogical elements for both approaches have been informed by education scholarship. Below is a table outlining the common pedagogical elements in the self-directed and facilitator-led VEGA education interventions (Table 1).

Table 1: Pedagogical Elements of Self-Directed VEGA (i.e., experimental arm) and Facilitated VEGA (active control arm) Educational Approaches

Pedagogical Elements	Self-Directed VEGA (Experimental Arm)	Facilitator-Led VEGA (Active Control Arm)
Didactic Material[45]	Asynchronous reading	Synchronous lecturing
Deliberate practice[46, 47]	Case-Based Animated Simulations	Case-Based Role play
Enabling learning tools [48]	Virtual Patients, Clinical Handbook, Clinical Scripts	Virtual Patients, Clinical Handbook, Clinical Scripts
Test-enhanced learning [43]	Individual multiple-choice questions with response feedback	Group-based polling (i.e., multiple-choice) and feedback.

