6.2 Data Safety Measures

6.2.1. Data Access

The Research Coordinator, in collaboration with the Principal Investigator, will oversee all aspects of the data collection and management at the Offord Centre for Child Studies at the Ron Joyce Children's Health Centre located at [name] and [name],

Centre of Excellence VEGA Training and Research Project

both located in Hamilton. Access to data will be limited to certain members of the research team based on the type of data, listed below:

Participant treatment allocation: The list of participant's IDs with their study arm allocation after randomization will only be accessed by the facilitators and the Research Coordinator. The research assistant will not have access to study arm allocation. The facilitators of the VEGA training sessions will know which participants have been selected to complete the facilitator-led VEGA as they will be carrying out the workshops. VEGA workshop facilitators include regulated health professionals who are bound to principles and limits to confidentiality outlined by their regulatory body. All facilitators will sign a research confidentiality agreement prior to their involvement in the study.

Identifying information: The research coordinator, research assistant, and [name] will have access to identifying information in the participant tracking document. The participant tracking document that matches all participant unique IDs will be stored on a fully encrypted document on a secure McMaster server.

The research assistant will need access to the participant tracking document to contact participants for quantitative surveys and screening calls. The research coordinator will need the participant tracking document to coordinate the training component with participants and qualitative data collection.

The VEGA team will have access to identifying information, specifically participants' names and contact information. This information will be required for registration for online modules and monitoring participant's completion of them.

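### The prior-VEGA exclusion names registration only, so a provider who took VEGA in a workshop without registering stays eligible and has no pre-exposure baseline

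*Combined protocol and SAP*

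**What the plan says.** Section 2.2.1 sets two exclusions. The first is "HSSPs who have previously registered to access VEGA materials". The second is "HSSPs who are currently enrolled in or expected to enroll in any other educational intervention focused on family violence" during the study period. Neither mentions past attendance at a VEGA workshop, and the second looks only at current or expected training.

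VEGA has two routes. Section 1.1 states: "VEGA can be completed as a self-directed learning opportunity or in a workshop that is led by two trained facilitators". Section 2.2.4 describes the facilitator-led form as delivering the "content as a virtual or face-to-face workshop", and then limits this trial's own workshops to the virtual form.

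Registration is described for one route. For self-directed VEGA, section 2.2.4 says "Individuals will register to access the VEGA Education Resources site at" a stated web address. Section 6.2.1, on the names and contact details passed to the VEGA team, says: "This information will be required for registration for online modules and monitoring participant's completion of them". The workshop description ("The AC intervention will be facilitated via Zoom technology, by two trained facilitators") contains no registration step.

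Section 2.2.2 says the screening questionnaire will "contain a series of questions to determine the eligibility of providers for the study, defined by the inclusion and exclusion criteria above". Section 3.2.2 adds a Time 1 question on earlier IPV and CM training. It is not described as asking about VEGA, and no exclusion or analysis in section 4.1 refers to it.

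Since March 2023 the trial has one arm of 40. The secondary hypotheses in section 2.1.3 concern change from Time 1 to Time 2 and from Time 1 to Time 3.

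**The concern.** The exclusion appears meant to secure participants who are new to VEGA, but it uses registration as a stand-in for exposure. The stand-in fits the online route and, as far as the documents show, may miss the workshop route.

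A past workshop attendee would complete the Time 1 knowledge, preparedness and self-efficacy measures after having met the same content. Such a person would plausibly start higher and gain less, which pulls the mean change towards zero. In the two-arm design, randomization would have tended to balance prior exposure between the arms. In the one-arm design, change from Time 1 is the only contrast left, and section 2.1 still aims to produce initial estimates of effectiveness from it.

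**Working it through.** **Step 1. Follow a past workshop attendee through the rules.**

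- First exclusion (2.2.1): applies only if the person registered to access VEGA materials. Registration is described for the site and online modules (2.2.4, 6.2.1) and not for the workshop.
- Second exclusion (2.2.1): does not apply, because the training is in the past.
- Screening (2.2.2): built from these same criteria, so as described it adds no further barrier. The form itself is not in the documents.
- Time 1 training-history question (3.2.2): comes after consent, is general, and leads to no exclusion or adjustment.

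An attendee who never registered therefore passes every described step.

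**Step 2. The plan's own figure.** Section 4.2 gives 80% power for 40 per arm at 0.5 to 0.6 SD, for the former two-arm comparison. Alpha and sidedness are not stated; I assume 0.05 and use the normal approximation. The detectable difference is (z_alpha + z_power) × √(2/40).

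- One-sided: 0.556 SD, inside the stated range.
- Two-sided: 0.626 SD, just outside it.

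The present point does not depend on that figure. I take only 0.5 SD from it, as a convenient size for the illustration.

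**Step 3. Illustrate the dilution.** All of these inputs except n are assumptions:

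- d = 0.5, the true mean change in unexposed providers, in SDs of their change score
- f = share of enrollees already exposed
- r = fraction of the gain that exposed enrollees still make
- n = 40 (section 4.2)

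Mean change = d × [(1 − f) + f × r].
Variance of change = 1 + f(1 − f) × [d(1 − r)]².
Power is for a paired t-test, two-sided 0.05, at mean ÷ √variance.

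| f (number of 40) | mean, r = 0 | power, r = 0 | mean, r = 0.5 | power, r = 0.5 |
|---|---|---|---|---|
| 0 (0) | 0.500 | 86.9% | 0.500 | 86.9% |
| 5% (2) | 0.475 | 83.0% | 0.4875 | 85.1% |
| 10% (4) | 0.450 | 78.4% | 0.475 | 83.2% |
| 20% (8) | 0.400 | 67.7% | 0.450 | 78.9% |

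Worked line, f = 10% and r = 0: mean = 0.5 × 0.9 = 0.45; variance = 1 + 0.09 × 0.25 = 1.0225; standardized change = 0.45 ÷ 1.011 = 0.445; power 78.4%.

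**Step 4. Scale.** The standard error of a mean change with n = 40 is 1/√40 = 0.158 SD. The 0.05 SD shift at f = 10%, r = 0 is 0.05 ÷ 0.158 = 0.32, about a third of one standard error. If f = 0 there is no effect.

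**The case against.** The criterion speaks of registering for VEGA materials, not of web registration. Workshop participants use materials too: Table 1 in section 2.2.4 lists virtual patients, a clinical handbook and clinical scripts for both formats. Attendees may have to register for these, and the unseen screening form may ask about workshops. No document shows that a workshop-trained provider exists in this population, and section 1.1 calls the resources novel. The outcomes affected are secondary and exploratory, any attenuation works against the hypothesis of an increase, and the shift is small beside sampling error. The Time 1 training question may identify some exposed people.

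Most of this stands, and it limits the size of the point. It does not close the gap: the only registration the protocol describes is for the site and its modules, and a criterion that can be read two ways should be clarified.

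A reader might infer more than the documents support:

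- *The trial's baseline as a whole is unsound.* Only the Time 1 scores of previously exposed enrollees are affected, and none is shown to exist.
- *The 70% completion criterion is inflated.* Nothing shows that trained providers are more willing to finish. They could equally be less willing to repeat about three hours of familiar content.
- *People from this trial's own facilitator-led arm could re-enter.* The documents do not say that a workshop was held, and the Research Coordinator holds the allocation list.
- *Providers could register between screening and Time 1.* No described step rechecks this, but that it happens is conjecture.
- *Excluding people who registered but never opened a module is a mistake.* It is a conservative rule that can be checked.

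**Conclusion.** The gap in wording is real. As written, section 2.2.1 leaves eligible a provider who took VEGA in a workshop without registering, and no other described step removes or flags that person. For such a participant, Time 1 is not a pre-exposure measurement, and the likely effect on the secondary change estimates is attenuation.

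The size cannot be derived from the documents and may be zero. It depends on the unknown share of exposed enrollees and on how much they still gain; each one is 1/40 = 2.5% of the sample. The primary outcomes in section 2.1.3 (recruitment, consent, completion and missing data) do not use Time 1 scores as a baseline. The point is worth acting on because the correction is cheap and protects the only contrast that the one-arm design has left.

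**What to change.** 1. In section 2.2.1, keep "HSSPs who have previously registered to access VEGA materials" and add: *or attended a VEGA workshop*.
2. Ask about registration and workshop attendance explicitly at screening.
3. Add VEGA as a named option to the existing Time 1 training-history question (section 3.2.2), in the part that records training received, because the part on the most helpful environments is capped at three.
4. In section 4.1.3, prespecify a sensitivity analysis of change from Time 1 that leaves out anyone who reports earlier VEGA exposure.

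The registration criterion should not be replaced by one based on having opened or completed content, because a registration list cannot verify that. A check of names by the VEGA team is not needed either. Section 6.2.1 gives that team names for module registration and completion monitoring, so eligibility vetting would be a new use that may need further permission, and no workshop attendance list is documented.

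Cost: one phrase, one screening item, one answer option and one short analysis. The downside is that a few workshop attendees may be turned away in a trial that already reports low enrolment (section 2.1).

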2.2.2 Informed Consent

Once a provider has initiated contact with the research team, the research assistant (RA) will, depending on the participant's preference, either arrange a telephone call to discuss the study and ask eligibility and demographic screening questions or send them a link to the screening & demographics questionnaire hosted on REDCap [see “Step 3: Initial Contact from Participant & Arranging Screening and Demographics Questionnaire” in “CoE_VEGA_EmailScripts_V8_12MAY2023”]. During the call, the RA will first give a short description of the training and research components of the study with the opportunity of providers to ask questions. If participants choose to self-complete the questionnaire online, there will also be a short description of the study before participants complete the questionnaire on REDCap. The screening and demographics questionnaire will contain a series of questions to determine the eligibility of providers for the study, defined by the inclusion and exclusion criteria above. It will also ask a series of sociodemographic questions [for eligibility and demographic questions, see “Appendix A: Screening Eligibility and Demographic Questionnaire REDCap Form” in “CoE_VEGA_ScreeningCallScript_V7_03APR2023”]. If completing measures over the phone, the provider's answers will be entered by the RA into REDCap. We will obtain written consent from providers to keep their responses to the screening and demographics questionnaire should they end up being ineligible or do not end up participating in the study. This is for the purpose of comparing those who end up participating to those who do not end up participating to understand

Centre of Excellence VEGA Training and Research Project

if our criteria are potentially excluding a particular group of people or if those who do not end up participating belong to a particular group.

After completing the eligibility and demographic questions, providers will be informed of their eligibility for the study. This communication will occur via phone [see pg. 2-3 of CoE_VEGA_ScreeningCallScript_V7_03APR2023] or email [see pg. 4-5 of CoE_VEGA_EmailScripts_V8_12MAY2023] based on the participant's preference.

Providers will be emailed a link to an electronic version on REDCap and a pdf version of the Letter of Information/Consent (hereafter referred to as “consent form”) [see “Step 4: Electronic Consent Form” in “CoE_VEGA_EmailScripts_V8_12MAY2023”]. Together, the RA and practitioner will review the Letter of Information/Consent [see “CoE_VEGA_ConsentForm_V8_03MAR2023”] per International Conference on Harmonization – Good Clinical Practice (ICH-GCP) guidelines and institutional policy. Providers will be encouraged to take as much time as they need to review the consent form and will be provided the opportunity to speak with the RA on the phone if they have any questions at any time. The consent form will outline the purpose of the study, the commitment that will be required of participants, the potential risks and benefits associated with study participation, and all the measures the research team will take to protect their confidentiality. It will be the responsibility of the person obtaining consent to ensure that participants understand the extent of their role in the research. The RA obtaining consent will foster an open exchange of information, encouraging potential participants to ask questions prior to research involvement, to review the pdf copy of the consent form at any time, and to continue to ask questions that may arise at any point during the study if they participate. Details of the consent form will be presented in simple language as approved by the Research Ethics Board (REB) of the institutions involved. If the participant indicates they are ready to complete the consent form, they will be asked to select the option “I agree to participate in the study,” to enter their full name and the date, and electronically sign in the consent form on REDCap. After completing this and submitting on REDCap, the RA will download a PDF copy of the consent form with the participant's responses from REDCap. They will add the following using Adobe PDF software: “Consent form administered by,” and print their name, electronically sign, and date. If the participant prefers to provide written consent using the PDF copy of the consent form, we will make this option available to them and they can print their name, sign and date, and submit this to the RA or LPI by email or to the LPI by mail. The RA will print their name, sign and date, on this form where it says “consent form administered by.”

Once the participant provides written consent, the RA will send the baseline (Time 1) questionnaire. The Time 1 questionnaire will be sent via an email that will contain a link to the assessment measures hosted in REDCap. Providers will be asked to complete measures within one week of receipt of the email.

